8. CLINICAL INVESTIGATION INTERVENTION

8.1 Identity of the medical device under investigation

In this study, the following medical device will be investigated:

Steriwave™ Nasal Photodisinfection System
Ondine Biomedical Inc., Vancouver, Canada.

It consists of three parts with the corresponding model numbers:

SW4000 Light Source
SW3200 Nasal Light Illuminator
SW3100 Formulation Applicator
Photosensitizer: methylene blue

SW4000 Light Source

Class 1 Laser Device that generates red light consisting of 2 channels of 700 mW, 664 nm light (continuous wave) used to activate the disinfecting formulation.

SW3200 Nasal Light Illuminator

Light diffuser tips are attached to fiber optic cables that deliver red light through a plug-in connection to the Light Source. Diffuser cables are labeled with an "L" for the left nostril and "R" for the right nostril. Single-use item.

SW3100 Formulation Applicator

Sealed tubular package containing a formulation-saturated swab that extends from the detachable lid. The proprietary formulation includes methylene blue and chlorhexidine gluconate, along with several inactive ingredients. Single-use item.

8.1.1 Experimental intervention (medical device)

The intervention consists of the following steps:

1. Swabbing the formulation applicator (soft swab pre-saturated with the photosensitizer formulation) into patient's nostrils.
2. Connection of the nasal light illuminator to the light source and insertion of the nasal light illuminator into the patient's right and left nostrils.
3. Activation of the light source and illumination of the nose and nasopharynx for 2 minutes.
4. Repetition of steps 1.-3. to complete photodisinfection of all nasal regions.

Duration of treatment: 14 minutes

- pre-intervention nasal swab test (0.5 min)
- waiting time (3 min)
- nasal application of photosensitizer (0.5 min)
- 2min illumination
- Repetition of photosensitizer application (0.5 min)
- 2 min illumination
- Waiting time (5 min)
- Post-intervention nasal swab test (0.5 min)

All treatment steps follow the CE-labeled instructions for use of the medical device. There are no deviations from the commercial product. The corresponding part of the instructions for use provided by the manufacturer is shown in **Figure 2**.

The procedure will be performed by the investigators (physicians or clinical study nurses with special training provided by the manufacturer of the medical device).

All investigators and clinical study nurses have been trained by the manufacturer in the use of the medical device and its components. All consumables will be disposed of in accordance with hospital hygiene standards and treated as contaminated with infectious materials. The light source will be wiped down with the standard disinfectant solution provided by the hospital. Before starting the intervention, the optical power output will be checked with the manufacturer's approved power tester to ensure that the optical output power meets the technical specifications.

Figure 2: Steriwave™ instructions for use (pages 6 and 7; Ondine Biomedical Inc.)

PROCEDURE

Use the following instructions to perform the nasal photodisinfection procedure.

SETUP

- 1 Position the Light Source to ensure the light diffuser tips of the fiber optic cable can reach the patient's nose without tension. Ensure Light Source air vents are not obstructed.
- 2 Connect the Light Source power cord to mains power outlet. Ensure cord is not a tripping hazard.
- 3 Press the Standby button on the Light Source. The indicators will flash on the LED display. Any startup errors will display on the LED display and an audible tone will sound. If there are no errors, the Connector Indicator will flash, indicating system is ready to attach NLI.

NOTE: In case of an emergency, disconnect the power cord from the Light Source.

PREPARING THE PATIENT

- 4 Position the patient in a seated, Semi-Fowler's, reverse-Trendelenburg, or supine position. Avoid Trendelenburg, if possible.
- 5 Have the patient blow their nose thoroughly and don a protective bib and protective eyewear.

6 SW9000-001 Rev E

- 10 Connect the NLI to the Light Source by plugging into the connector block until it double-clicks. The Connector Indicator will stop flashing on the LED display and the Start button will flash, indicating the Light Source is in READY mode.

NOTE: The NLI must be properly connected for the Light Source to be activated.

- 11 **Posterior Illumination:** Gently insert both light diffuser tips into the nasal passages, **orienting the light diffuser tips to point towards the forehead.** The light diffuser tips MUST be kept inserted during the entire treatment cycle.

NOTE: Diffuser cables are identified with an "L" or "R" indicator, to designate the left or right patient nostril. Use the same cable for the same nostril throughout the complete treatment, to avoid potential cross-contamination of pathogens between nostrils.

- 12 Press the flashing Start button to initiate light illumination. The circular indicator on the LED display turns off when the 2-minute illumination cycle is complete. An audible tone will sound, and illumination will automatically stop.

[figure not shown]
- 13 Remove the light diffuser tips from the patient's nose. Take care to prevent the light diffuser tips from contacting other surfaces (e.g., place the connector block on the accessory hook on the side of the Light Source).

- 14 Use two new Formulation Applicators to reapply formulation to each of the anterior nasal passages, with special care taken to get good coverage in the most anterior nasal pocket area (the tip of the nose).

- 6 Open the Formulation Applicator by:

a. Squeeze the tube directly on the junction until tube "pops" open. Ensure the tube is held vertically and aimed away from the operator's face to avoid splashing formulation.

b. Gently rock the stem back and forth to extract the swab.

- 7 Insert the single-use swab approximately 2-3 cm deep into one nostril. Swab the inside of the nasal passage to deposit formulation uniformly and generously in all areas below the turbinates, with special care taken to get good coverage in the most anterior nasal pocket area (the tip of the nose). Repeat with a second swab in the other nostril.

[figure not shown]
- 8 Dispose of the used swabs per standard hospital protocol for biohazardous waste.

APPLYING THE NASAL LIGHT ILLUMINATOR

- 9 Open the NLI packaging. DO NOT allow the NLI light diffuser tips to contact ANY surface before inserting into the patient's nose.

INSTRUCTIONS FOR USE

- 15 **Anterior Illumination:** Gently insert a light diffuser tip into each nostril and **orient the tips anteriorly and medially toward the tip of the nose.**

- 16 Press the flashing Start button to initiate illumination.

- 17 Upon completion of the 2-minute illumination cycle, remove the light diffuser tips from the patient's nostrils.

- 18 Disconnect the NLI from the Light Source and dispose of all single-use items (NLI and FAs) per standard hospital protocol for biohazardous waste.

NOTE: Temporary tissue staining beneath the nose may be removed with an alcohol wipe or soap and water.

- 19 Return the Connector Block to the accessory hook on the side of the Light Source.

STANDBY

- 20 Press the Standby Button to place the Light Source into SLEEP mode.

SHUT DOWN

- 21 Disconnect the power cord from mains power to move the Light Source.

NOTE: In case of emergency, always disconnect the power cord from the Light Source.

7 SW9000-001 Rev E

8.1.2 Control intervention (standard/routine/comparator)

The control intervention consists of the following steps:

“Differences to experimental group in bold”

1. Swabbing the formulation applicator (soft swab pre-saturated with the photosensitizer formulation) into patient's nostrils.
2. Connection of the nasal light illuminator to the light source and insertion of the nasal light illuminator into the patient's right and left nostrils.
- 3. No activation of the light source. Waiting for 2 minutes.**
4. Repetition of steps 1.-3. to complete control intervention

Duration of treatment: 14 minutes

- pre-intervention nasal swab test (0.5 min)
- waiting time (3 min)
- nasal application of photosensitizer (0.5 min)
- **2 min waiting “control intervention”**
- Repetition of photosensitizer application (0.5 min)
- **2 min waiting “control intervention”**
- Waiting time (5 min)
- Post-intervention nasal swab test (0.5 min)

8.1.3 Nasal swab testing

The nasal swab tests for microbial analysis are performed in both nostrils with the same nasal swab probe to allow for pooled microbial analysis of both nostrils' colonization status in one swab test.

The same swab testing procedure is used for the pre-intervention nasal swab (3 minutes before intervention), the post intervention swab (5 minutes after intervention), the 2 days swab for the midface trauma subgroup and the follow-up swab on day 14 (+/-1) after intervention.

[figure not shown]
Storage and transfer of swabs is according to routine diagnostics of Institute for Medical Microbiology University of Zurich, [name], head of department [name]. med. Dr. phil. [name].

8.1.4 Labeling and supply

All consumables are pre-labeled by the manufacturer. Since the control group receive the same application of consumable (photosensitizer formulation), no additional labeling is needed. There are no deviations from the commercial products.

The manufacturer has provided two identical medical devices and the necessary consumables to perform 1'000 interventions. Replenishment during the study is not required as only 500 participants are to be included in this study. The light source has been validated for correct performance characteristics. The single-use formulation applicator (soft swab pre-saturated with photosensitizer) has been supplied by the manufacturer via approved carriers with itemized bills of lading. All consumables are stored in a controlled, secured location at room temperature. The formulation is non-sterile and is provided in the form of individually packaged, pre-saturated swabs. The formulation is labeled according to the manufacturer's standards (see **Figure 3**).

Figure 3: Formulation applicator (pre-saturated nasal swabs)

8.1.5 Storage conditions

The medical device and all required consumables are stored in a controlled, secured location at room temperature. The consumables are packed in a carton box for light protection. No reconstitution or mixing is required. The products are not sterile. Any consumables not used during the study will be returned to the manufacturer for further processing.

8.2 Discontinuation or modifications of the intervention

In case of an immediate adverse effect or upon the subject's request during the intervention, the device will be immediately removed from the patient. No modifications of the intervention are possible as the medical device only operates with the pre-defined settings.

8.3 Compliance with clinical investigation intervention

Subject compliance during the intervention will be monitored by the principal investigator or his designee as all patients will be observed during the light treatment.

8.4 Data collection and follow-up for withdrawn subjects

The reason for withdrawal will be noted in the CRF as described in chapter 7.4. In case of withdrawal, no further data will be collected. If the reason for the withdrawal is any problem related to the safety or performance of the medical device, the principal investigator will ask the subject for permission to follow their status and condition outside of the study. The data collected at the time of withdrawal will be used for statistical analysis in accordance with Art. 3 Abs. b ClinO-MD and subsequently anonymized. All biological material will be destroyed after evaluation.

8.5 Clinical investigation specific preventive measures

There are no specific preventive measures required for the subjects and no specific rescue medication. As the light is not harmful to the eyes, wearing protective goggles is not mandatory.

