2.2 Categorization of the investigation

This investigation is a clinical trial with a medical device. It falls under risk category A1: minimal risk. The health-related study intervention entails only minimal risks and burdens. The rationale for this classification is as follows:

- The medical device to be investigated in this study bears a mark of conformity (CE marking) in accordance with Article 13 MedDO (Medical Devices Ordinance).
- The medical device is used in accordance with the instructions for use.
- In Switzerland, it is not prohibited to make the medical device available on the market, to put it into service, or to use it.
- Participants will not undergo any additional invasive or stressful procedures as part of this study or need additional consultations.
- UDI 081000287SW4000RF

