3.2 Identification and description of the investigational medical device

In this study, the following medical device will be tested:

Steriwave™ Nasal Photodisinfection System
Ondine Biomedical Inc., Vancouver, Canada.

It consists of three parts with the corresponding model numbers (shown in **Figure 1**):

SW4000 Light Source
SW3200 Nasal Light Illuminator (single-use)
SW3100 Formulation Applicator (single-use)
photosensitizer: methylene blue

Figure 1 (Steriwave™ instructions for use, page 5; Ondine Biomedical Inc.)

COMPONENT FUNCTIONS

LIGHT SOURCE

The Light Source generates the red light used to activate the disinfecting formulation. The Light Source controls function as follows:

Buttons

[figure not shown]
[figure not shown]
Buttons	Function	Action
	Standby	Press to initialize the Light Source. Press to reset the Light Source.
	Start	The Start button will flash when the Light Source is in READY mode. Press the Start button to begin illumination.
	Stop	During illumination, the Stop button may be pressed at any time to stop light emission.

LED Display

Indicator	Indication	Action required
	Connector Symbol Flashing	Connect the NLI to the Light Source. The indicator will disappear when the NLI is properly connected.
	Blue Snowflake Illuminated	Light Source is too cold. Allow the Light Source to come to room temperature.
	Yellow Attention Illuminated	Error – Light Source operation is outside nominal ranges. Press Standby to reset the Light Source. If error persists, contact manufacturer for assistance.

[figure not shown]
Connector Block & Umbilical Cable – Type B Applied Part, connects the Light Source to the NLI.

Mains Power Cord (hospital grade) – connects the Light Source to electrical power.

[figure not shown]
NASAL LIGHT ILLUMINATOR (SINGLE-USE)

Type B Applied Part
NLI delivers the red light illumination to the patient's nose.
Light diffuser tips – provide comfort end-points to the cable.
Fiber optic cable – delivers the red light illumination.
Connector – provides the cable connection to the Light Source.

FORMULATION APPLICATOR (SINGLE-USE)

Single-use tube containing formulation applicator swab – provides disinfection photosensitizer formulation.

PATIENT EYE PROTECTION

Eyewear – Protects patient's eyes from formulation splatters or accidental eye contact of NLI.

INSTRUCTIONS FOR USE

SW9000-001 Rev E | 5

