The medical device bears a conformity marking (CE label) and is thus approved for medical use. Its intended use is aPDT of the nose and nasopharynx after topical application of a photosensitizer (methylene blue). No deviations from the original CE-marked instructions for use will be made in this study. No changes will be made to the design of the device.

The nasal light illuminator and the formulation applicator preloaded with the photosensitizer, which both are single-use disposable products, are the two parts of the device that get in contact with human tissue and body fluid (nasal secretion).

The manufacturer has provided training on the use of the medical device. All investigators and study personnel involved in the use of the medical device have been sufficiently trained and are experienced in the use of the device. All investigators and all members of the clinical study personnel have been provided with a copy of the instructions for use.

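### Section 8.5 makes goggles optional because the light is harmless, but the instructions prescribe eyewear against splatter and illuminator contact, which can occur in both arms

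*Combined protocol and SAP*

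**What the plan says.** Section 8.5 states that subjects need no specific preventive measures, and continues: "As the light is not harmful to the eyes, wearing protective goggles is not mandatory". No other reason is given.

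The protocol reproduces part of the manufacturer's instructions for use. In Section 3.2 (Figure 1), the entry on patient eye protection says that eyewear shields the patient's "eyes from formulation splatters or accidental eye contact of NLI" (NLI is the nasal light illuminator). In Section 8.1.1 (Figure 2), step 5 reads: "Have the patient blow their nose thoroughly and don a protective bib and protective eyewear". Step 6a tells the user to aim the tube away from the operator's "face to avoid splashing formulation".

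Three places commit the trial to these instructions:

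- Section 2.2, as one of the grounds for category A1: "The medical device is used in accordance with the instructions for use".
- Section 3.2: "No deviations from the original CE-marked instructions for use will be made in this study".
- Section 8.1.1: "All treatment steps follow the CE-labeled instructions for use of the medical device".

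The control procedure in Section 8.1.2 uses the same swabs and also includes "Connection of the nasal light illuminator to the light source and insertion of the nasal light illuminator into" both nostrils. Only the activation of the light is left out. Section 9.3.2 states that the patient is already under general anesthesia when this is done.

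**The concern.** A preventive measure named by the manufacturer is made optional on a ground that has nothing to do with its stated purpose. Whether the light is safe for the eyes does not bear on whether a saturated swab can splatter or a diffuser tip can touch the eye.

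The setting adds weight. An anesthetized patient cannot blink, turn away or report a splash. Section 8.2 provides for stopping at once on an adverse effect or at the subject's request, and the second of these safeguards is not available here.

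What is at stake is the safety of subjects and the consistency of the protocol with itself. It is not claimed that the A1 category would change or that the treatment comparison is biased.

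**Working it through.** The plan gives no figure on this point to reproduce. The check is a comparison of texts, followed by a count of exposure and a rough bound on risk.

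**Texts side by side**

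| Question | Section 8.5 | Reproduced instructions |
|---|---|---|
| Is eyewear to be worn? | Optional | Yes, an imperative step with no exception in the reproduced pages (step 5) |
| Which hazard is considered? | Light | Formulation splatter and contact with the illuminator (Figure 1) |
| Is light given as a reason? | Yes, the only one | No |

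The reason in Section 8.5 addresses neither hazard in the right-hand column. Section 3.4 also calls the light harmless to the eyes. That statement is not disputed, but it does not answer the question.

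**Is the measure provided elsewhere?** The step lists in 8.1.1 and 8.1.2 do not mention eye protection. The risk-mitigation paragraph in Section 3.7 names only the exclusion of patients with known allergies. No section describes taping or covering the eyes.

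**Do both arms carry the hazards?** Yes. Formulation and illuminator are used identically, and only the light differs. In the control arm no light is emitted, so the rationale in 8.5 is irrelevant to half of the patients.

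**Exposure** (Section 3.5 for the dose, Figure 2 for the steps, Section 7.3 for the numbers)

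- Applicators per patient: 2 nostrils × 2 rounds = 4, and 4 × 1.5 ml = 6.0 ml of formulation.
- Applicator openings in the trial: 208 × 4 = 832, of which 104 × 4 = 416 in the control arm.
- Diffuser-tip insertions: 2 tips × 2 cycles × 208 = 832, again 416 in the control arm.

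These are counts of use, not of harm. Because eyewear is optional and not forbidden, the number of patients left unprotected is unknown.

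**Rough bound on risk** (Section 3.7, Table 2)

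The documents give no rate of splatter or eye contact. The nearest entries are watery eyes (6) and swelling in the eye (1).

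- Reports: 6 + 1 = 7.
- Rate: 7 / 49,313 = 1.42 per 10,000 treatments.
- Exact Poisson 95% limits for 7 events give 0.57 to 2.92 per 10,000.
- Expected in 208 patients: 208 × 7 / 49,313 = 0.030 (0.012 to 0.061).

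This is a weak proxy. Neither entry is attributed to splatter or contact, the setting was industrial, and the protocol does not say whether eyewear was worn there. If it was, the rate says nothing about leaving it off.

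**The case against.** Several points can be made for the plan.

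- **Step 6a is about the operator.** It protects the operator's face while the tube is opened, and the protocol does not say where tubes are opened relative to the patient. This stands. Step 6a shows only that splashing is foreseen, and the 832 openings should not be read as 832 exposures of the patient's eyes. The hazard to the patient's eyes rests on Figure 1, which names it directly.
- **Step 5 presumes an awake patient.** Someone under anesthesia cannot blow the nose or put on eyewear unaided. True, but staff can place eyewear or a cover on the patient. Only pages 5 to 7 of the instructions are reproduced, so a separate provision for anesthetized patients cannot be ruled out.
- **The instructions are already part of the protocol.** Section 8.1.1 says they are followed and reproduces step 5, and Section 8.5 permits eyewear. A general statement of adherence does not, however, override an explicit sentence saying that the item is not mandatory. Staff reading both would have conflicting directions.
- **The eyes may be covered anyway, and an anesthetized patient will not move into the tip.** Both are plausible, but the protocol states neither, and the second does nothing about splatter. Eye symptoms could be picked up in the day 1 and day 14 surveys, but that is detection, not prevention.
- **The risk is small.** This stands. Section 3.4 reports no serious adverse events in more than 150,000 treatments, and the proxy above is low. It limits the priority of the point without making the rationale in 8.5 correct.

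**Conclusion.** The concern holds. Section 8.5 relaxes a manufacturer-named protection for a reason that does not meet its purpose, for anesthetized patients in both arms, and against the protocol's own statements that the instructions are followed.

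The likely harm is small: about 0.03 eye-related reports expected in 208 patients (95% limits 0.01 to 0.06), if the Table 2 rate carries over. That transfer is an assumption, because eyewear use in those data is unknown. The conclusion does not depend on the figure. It rests on the protocol text and on reading an imperative step in the instructions as a requirement. It would weaken if the pages not reproduced exempt anesthetized patients, or if the eyes are routinely covered by other means that the protocol does not mention.

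This should be corrected before use, but it has no bearing on sample size, power or the primary analysis.

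**What to change.** Delete the sentence on goggles in Section 8.5. In the step lists of 8.1.1 and 8.1.2, add one line: eye protection (eyewear or an equivalent eye cover) is placed on every patient before the first applicator is opened and stays in place until the illuminator is removed after the second cycle. Allowing an equivalent cover accommodates ordinary anesthetic practice while still protecting against both named hazards.

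As a minor clarification, state how the rest of step 5 is handled, for example nose-blowing before induction and when the bib is placed.

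The cost is one sentence removed, one line added to each step list, and a few seconds of preparation per patient. The analysis and the sample size do not change.
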